4.2.1.7 Supplementary Analyses of the Primary Endpoint

4.2.1.7.1 Supplementary Analysis of the Primary Endpoint – targeting the impact of PEOT due to different reasons

A supplementary analysis for BICLA response is to assess the impact of PEOT due to different reasons by combining composite, treatment policy and hypothetical strategies to handle PEOT due to different reasons. That is, intercurrent events of PEOT due to lack of therapeutic response (after blinded review of the discontinuation reasons, see Section 3.3.7 for details) will result in a non-responder (NR) status per composite strategy. PEOT due to COVID lockdown will be handled per hypothetical strategy. PEOT not due to lack of therapeutic response or COVID lockdown will be ignored per treatment policy. RM and death will still be handled using composite strategy and will be imputed as non-responders from the time such ICEs occur up to week 52. More details on the derivation rules are specified as below.

For subjects with intercurrent events of RM, death and PEOT due to lack of therapeutic response, they will be imputed as non-responders from the time such ICEs occur up to Week 52. For subjects with PEOT due to COVID lockdown, data after PEOT will not be used and will be imputed. Intermediate and terminal missing values for BILAG-2004, SLEDAI-2K and PGA will be imputed separately for each BICLA component using multiple imputation under the assumption of missing at random. Missing values of BICLA

are imputed based on the imputed values of the BILAG-2004, PGA and SLEDAI-2K components.

For each outcome and visit, 100 imputations are generated by randomized treatment group. The procedure is initiated with a seed of 12345. For analysis, each imputed dataset is analyzed separately using the CMH approach described in Section 4.2.1.5, and the single estimates is combined using PROC MIANALYZE. Each component is imputed as follows:

- BILAG-2004 is imputed as a binary variable reflecting the BICLA criterion, i.e., “Reduction of all baseline BILAG-2004 A to B/C/D and baseline BILAG-2004 B to C/D, and no BILAG-2004 worsening in other organ systems, as defined by ≥ 1 new BILAG-2004 A or ≥ 2 new BILAG-2004 B”. This binary BILAG variable for participant i at visit t is modelled as $BILAG_{i(t)} \sim \text{Binomial}(1, \pi_{i(t)})$ where $\pi_{i(t)} = \theta_1 BILAG_{i(t-1)} + \theta_0(1 - BILAG_{i(t-1)})$ for $t > 1$ and $\pi_{i(t)} = \theta_2$ for $t = 1$ (Week 4). Independent $\text{Beta}(1,1)$ priors are specified for θ_0 , θ_1 and θ_2 . 10,000 burn-in iterations are used, followed by 10,000 main iterations. Imputations are then taken from every 100th iteration of the main chain (i.e., after burn-in).
- SLEDAI-2K total score is imputed with PROC MI using the MCMC IMPUTE=FULL specification, and a VAR statement specifying the variables in order of visit. Specify MINIMUM=0 to ensure imputed values are non-negative. Specify MAXIMUM=105 to avoid imputation of values above the maximum possible score. 10,000 burn-in iterations to be used, with 100 iterations between each imputation.
- PGA will be imputed in the same way as SLEDAI-2K total score but using MAXIMUM=3 (instead of MAXIMUM=105).

The estimated treatment effect, corresponding 95% CI, and 2-sided p-value for the difference at Week 52 will be provided using the same method as presented in Section 4.2.1.5. 错误!未找到引用源。。

4.2.1.7.2 Supplementary Analysis of the Primary Endpoint – targeting the impact of PEOT

A supplementary analysis for BICLA response at week 52, using the CMH approach described in Section 4.2.1.5, is repeated removing the criterion of PEOT. Therefore, PEOT does not result in a NR status, RM is retained as part of the composite endpoint definition and thus results in a NR status. Death is imputed as NR from the time such events occur up to Week 52.

The estimated treatment effect, corresponding 95% CI, and 2-sided p-value for the difference at Week 52 will be provided using the same method as presented in Section 4.2.1.5.

4.2.1.7.3 Supplementary Analysis of the Primary Endpoint – targeting the impact of different discontinuation rates; based on tipping point analysis

In order to examine the impact of different discontinuation rates between treatment groups, a tipping point analysis will be performed if p-value for the primary analysis is ≤ 0.05 . This analysis will vary the assumptions about outcomes among the subsets of participants on the treatment arms who prematurely discontinue IP and can be described as:

- The proportions of participants achieving BICLA response will be analyzed using a Pearson's chi-squared test, thus the stratification factors that are used in the main analysis (CMH) will be disregarded. Since the strata will be balanced in respect of treatment assignment by virtue of the stratified randomization scheme used, the only impact of this simplification should be that the inferences from the unstratified analysis will be somewhat conservative.
- For the primary analysis, participants who prematurely discontinue IP having not received restricted medications prior to discontinuation of IP are by definition, imputed as non-responders. For this analysis, these participants will be altered from non-responder to responder in an iterative manner.
- At each step of the analysis one of these participants switches from not achieving BICLA response to achieving BICLA response, and the Pearson's chi-squared test is re-run. The results (statistical significance) are presented in a grid where the x-axis and the y-axis represent the added number of participants assumed to be achieving BICLA response for placebo and anifrolumab 300 mg, respectively. The region where the conclusion changes, will be considered as the tipping point.

4.2.1.7.4 Supplementary Analysis of the Primary Endpoint - targeting the impact of RM

A supplementary analysis for BICLA response, using the CMH approach described in Section 4.2.1.5, is repeated removing the criterion of RM. Therefore, this analysis does not consider participants as NR if they have used restricted medications. The PEOT is considered as NR and Death is imputed as NR from the time such events occur up to Week 52.

The estimated treatment effect, corresponding 95% CI, and 2-sided p-value for the difference at Week 52 will be provided using the same method as presented in Section 4.2.1.5.

4.2.1.7.5 Supplementary Analysis of the Primary Endpoint - targeting the impact of PEOT and RM

A supplementary analysis for BICLA response, using the CMH approach described in Section 4.2.1.5, is repeated removing both the criterion PEOT and RM. Therefore, PEOT and/or RM do not result in a NR status. Death is imputed as NR from the time such events occur up to Week 52.

The estimated treatment effect, corresponding 95% CI, and 2-sided p-value for the difference at Week 52 will be provided using the same method as presented in Section 4.2.1.5.

4.2.1.7.6 Supplementary Analysis of the Primary Endpoint - targeting the impact of being automatically classified as responder due to their baseline VAS and/or BILAG scores

A supplementary analysis using the CMH approach described in Section 4.2.1.5 is performed excluding from the analysis those subjects with no BILAG A or B at baseline, as well as participants with a baseline PGA VAS score > 2.7.

The estimated treatment effect, corresponding 95% CI, and 2-sided p-value for the difference at Week 52 will be provided using the same method as presented in Section 4.2.1.5

4.2.1.7.7 Supplementary Analysis of the Primary Endpoint – Time to BICLA response

Time to BICLA response sustained up to Week 52 is defined as the visit of first BICLA response which is sustained up to, and including, Week 52. Subjects without a BICLA response sustained up to Week 52 are censored at the date of last available BICLA assessment up to and including Week 52 during the double-blind treatment period. BICLA response is defined in Section 4.2.1.1.

The PEOT, RM and death are intercurrent events. Subjects with PEOT, RM and/or death will be considered NR (not achieving a sustained BICLA response) from the date they prematurely end treatment, take restricted medications or death respectively, through to and including Week 52. Subjects who are WDS status are handled by censoring the subject from the date of the WDS.

The supportive outcome of time to BICLA response sustained up to Week 52 is analyzed using a Cox proportional hazard models (using a profile likelihood approach with ties=Efron) including the covariates of treatment and the stratification factors. The estimated hazard ratios and corresponding CIs will be presented for the effect of the treatment group. Furthermore, the time to BICLA response sustained up to, and including, Week 52 will be presented as Kaplan-Meier plot including the number of participants at risk at each visit.

4.2.1.8 Subgroup Analyses

To explore the uniformity of the detected overall treatment effect on the primary endpoint (i.e., only for the primary estimand excluding the supplementary and sensitivity analyses), subgroup analyses may be performed for the following factors:

- Region (mainland China versus not mainland China)
- SLEDAI-2K score at screening (<10 points versus ≥ 10 points)
- OCS dose at baseline (<10 mg/day versus ≥ 10 mg/day prednisone or equivalent)
- Sex (male versus female)
- Age (≥ 18 to <65 versus ≥ 65 years)
- Onset of disease (adult versus pediatric onset)
- BMI (≤ 28 versus >28 kg/m²)
- IFN 4-gene test (high versus low)
- ADA Result (positive at any time, negative, persistently positive, positive with titer $>$ median of maximum titer)
- Baseline anti-dsDNA, C3 and C4 (at least one positive/abnormal, all negative/normal)

Treatment effect is estimated by the stratified CMH model. A forest plot reporting response rates, estimated differences with its 95% CI for treatment derived by the stratified CMH model is presented overall and by subgroups.

4.2.2 Key Secondary Endpoint - SRI (4)

4.2.2.1 Definition

The key secondary efficacy endpoint, the assessment of disease activity will be evaluated based on the difference in proportions between anifrolumab and placebo in SRI(4) response at Week 52. SRI(4) is defined as a participant meeting all the following criteria:

- Reduction from baseline of ≥ 4 points in the SLEDAI-2K will be derived as the sum of the scores for all items. A ≥ 4 points reduction is reached if the change from baseline is ≤ -4 .
- No new organ systems affected as defined by 1 or more new BILAG-2004 A or 2 or more new BILAG-2004 B items compared to baseline
- No worsening from baseline in participants' lupus disease activity, where worsening is defined by an increase ≥ 0.30 points on a 3-point PGA VAS

4.2.2.2 Derivations

Not applicable.

4.2.2.3 Handling of Dropouts and Missing Data

If any of the criteria mentioned in the Section 4.2.2.1 cannot be evaluated at any visit up to Week 52 (e.g., due to missing values), the data for that criterion will be imputed using LOCF and SRI(4) response is derived based on the complete data. This applies only once. Missing data after LOCF will be imputed as non-responder. For example, if any of the Week 52 criteria data is missing and Week 48 data is not missing, the missing Week 52 criteria data will be imputed using the corresponding Week 48 data. Otherwise, the participant is defined as a SRI(4) non-responder at Week 52.

4.2.2.4 Primary Analysis of Key Secondary Endpoint - SRI (4)

The same CMH approach as described in Section 4.2.1.5 for the primary endpoint is used to estimate the treatment difference between anifrolumab and placebo as well as the response rates. Nominal p-values will be presented for Week 52 only. Using the same CMH approach, longitudinal presentations of the results over time (i.e., for each post-baseline visit up to Week 52 during double blind treatment period) is created.

The estimated treatment effect, corresponding 95% CI, and 2-sided p-value for the difference at Week 52 will be provided using the same method as presented in Section 4.2.1.5.

4.2.2.5 Supplementary Analyses of Key Secondary Endpoint

A supplementary analysis to assess the impact of PEOT due to different reasons by combining composite, treatment policy and hypothetical strategies to handle PEOT due to different reasons is performed using the similar method as described in Section 4.2.1.7.1, where component of BILAG-2004 is imputed as a binary variable reflecting the SRI (4) criterion, i.e., “No new organ systems affected as defined by 1 or more new BILAG-2004 A or 2 or more new BILAG-2004 B items compared to baseline”.

Supplementary analyses targeting the impact of intercurrent events: PEOT and/or RM are performed following the strategy discussed in Section 4.2.1.7.2, 4.2.1.7.4 and 4.2.1.7.5.

An analysis to examine the impact of different discontinuation rates based on tipping point analysis is performed following the strategy discussed in Section 4.2.1.7.3 by replacing BICLA response by SRI(4) response, if the nominal p-value is ≤ 0.05 for the primary analysis of SRI(4).

4.2.2.6 Subgroup Analyses

The subgroup analyses will be performed for the following stratification factors, i.e.

- Region (mainland China versus not mainland China)
- SLEDAI-2K score at screening (<10 points versus ≥ 10 points)
- OCS dose at baseline (<10 mg/day versus ≥ 10 mg/day prednisone or equivalent).

The analysis methods are the same as described above for SRI (4) endpoint in Section 4.2.2.4.

4.2.3 Key Secondary Endpoint - OCS

4.2.3.1 Definition

The effect of anifrolumab versus placebo on the ability to reduce the OCS dose in participants with baseline OCS ≥ 10 mg/day prednisone or equivalent will be evaluated. A maintained OCS reduction is defined as meeting all the following criteria:

- Achieve an OCS dose of ≤ 7.5 mg/day prednisone or equivalent by Week 40.
- Maintain an OCS dose ≤ 7.5 mg/day prednisone or equivalent from Week 40 to Week 52

A maintained OCS dose is defined as no dose increase (i.e., no dose greater than the dose at Week 40 + 1 day) between Week 40 + 2 days and Week 52, inclusive. The date used for Week 52 is the date of last assessment used for efficacy analysis (SLEDAI-2K, PGA and BILAG) in the time window of Week 52 (as described in Section 3.3.2). If no such assessment falls into the respective time window, then the target date for the timepoint will be used instead.

The derivation of the prednisone equivalent daily dose is given in Appendix 7.4.

4.2.3.2 Derivations

The dose of OCS at Week 40 used in the evaluation of this endpoint is the dose on the date of Week 40 + 1 day.

The date used for Week 40 is the date of last assessment used for efficacy analysis (SLEDAI-2K, PGA and BILAG) in the time window of Week 40 (as described in Section 3.3.2).

4.2.3.3 Handling of Dropouts and Missing Data

If any of the conditions cannot be evaluated at Week 52 (e.g., due to missing values) the participant is considered as not reaching a maintained OCS reduction.

If there is no assessment in Week 40 window, then the target date for the timepoint will be used instead.

4.2.3.4 Primary Analysis of Key Secondary Endpoint - OCS

The same CMH approach as described in Section 4.2.1.5 for the primary endpoint will be used to estimate the treatment difference between anifrolumab and placebo in subjects with baseline OCS ≥ 10 mg/day prednisone or equivalent. Nominal p-value is presented for Week 52 only. For the stratified CMH analyses, the stratification factors will be reduced to SLEDAI-2K score at screening (< 10 points versus ≥ 10 points) and region (mainland China versus not mainland China).

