##### **Disease Characteristics**

6. Participants who have a diagnosis of paediatric or adult SLE according to the ACR 1997 revised criteria ([Stoll et al, 2004](#); [Tan et al, 1982](#); see [Appendix D](#)) for  $\geq 24$  weeks prior to signing the ICF.
7. Must be receiving at least one of the following standard therapy regimens at Screening:
  - (a) Oral prednisone (or equivalent) monotherapy:
    - Start date: minimum daily dose:  $\geq 7.5$  mg/day for at least 8 weeks prior to Day 1 (randomisation)
    - Must be stable for  $> 2$  weeks before Day 1 (randomisation)
    - Maximum daily dose:  $\leq 40$  mg/day
  - (b) Antimalarials and/or immunosuppressant(s) with or without OCS:
    - Permitted medications include: antimalarials, azathioprine, mycophenolate mofetil/mycophenolic acid, methotrexate, mizoribine, tacrolimus, and cyclosporine (Note: The combination of azathioprine and methotrexate is not allowed due to known safety issues. The combinations of tacrolimus/cyclosporine

with other immunosuppressants above should be avoided. Combination with antimalarials is allowed.)

- Start date:  $\geq 12$  weeks prior to signing the ICF.
- Must be stable  $\geq 8$  weeks prior to signing the ICF.
- The daily dose should follow the local medical practice and not exceed the maximum allowed daily dose:
  - Azathioprine:  $\leq 200$  mg/day.
  - Mycophenolate mofetil  $\leq 2$  g/day or mycophenolic acid  $\leq 1.44$  g/day.
  - Oral, subcutaneous (SC), or intramuscular methotrexate  $\leq 25$  mg/week.
  - Mizoribine  $\leq 150$  mg/day.
  - Tacrolimus  $\leq 0.2$  mg/kg/day or cyclosporine  $\leq 5$  mg/kg/day, monitoring of serum concentration may be performed at the discretion of Investigator where local practice guidelines mandate or in case of safety concerns.

(c) Oral prednisone (or equivalent) plus immunosuppressant(s):

- Start dates for OCS and immunosuppressants must be met.
- Stability requirements for each medication must be met.
- No minimum daily dose for OCS when in combination with immunosuppressants.
- Maximum daily dosages for each medication in (a) and (b) must not be exceeded.

8. Autoantibody-positive at Screening, as determined by the central laboratory, for at least one of the following:

- (a) Antinuclear antibody (ANA) immunofluorescent assay test (titer  $\geq 1:80$ ).
- (b) Anti-dsDNA.
- (c) Anti-Smith (anti-Sm).

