**Table 10 Example of OCS Tapering Schedule**

Time point	Initial Dose of Oral Prednisone or Equivalent			
	40 mg	30 mg	20 mg	10 mg*
Day 8	35 mg	27.5 mg	17.5 mg	10 mg
Day 28	30 mg	25 mg	15 mg	10 mg
Day 42	25 mg	20 mg	10 mg	10 mg
Day 56	15 mg	15 mg	10 mg	7.5 mg
Day 70	10 mg	10 mg	7.5 mg	≤ 7.5 mg
Day 84	7.5 mg	7.5 mg	≤ 7.5 mg	≤ 7.5 mg

\* Note: participants on OCS doses equivalent to 10 mg prednisone/day may tolerate tapering by 1 mg/day per visit rather than an abrupt drop from 10 mg/day to 7.5 mg/day. The stepwise tapering of OCS dose should be performed at the discretion of Investigator.

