4.2 Endpoint Analyses

This section covers details related to the endpoint analyses such as primary, key secondary and other endpoints including sensitivity and supportive analyses.

If not stated otherwise, change from baseline will be calculated as value at the respective time point minus value at baseline. The percent change from baseline is defined as change from baseline divided by baseline value multiplied with 100.

Intercurrent events are defined as events occurring after treatment initiation that affect either the interpretation or the existence of the measurements associated with the clinical question of interest. In this study the intercurrent events are:

- Restricted Medication use
- Premature End of Treatment
- Death.

If a patient observes an intermittent ICE of RM use (see Section 4.1.8.1), the ICE strategy of RM will be applied to the period defined.

Hereafter the intercurrent events of Restricted Medication use is referred to as RM, and Premature End of Treatment is referred to as PEOT. Additionally, Non-Response or Non-Responder are referenced as NR. PEOT is identified by the eCRF form DOSDISC “Discontinuation of Investigational Product”). Subjects with IP being prematurely and permanently discontinued are considered as PEOT status from the date of last IP dose administered + 28 days.

RM are identified from the start date of the concomitant medication use reported in the CM form meeting the criteria to be classified as RM. The start date for RM status is identified during the restricted medication review – see Appendix 7.4.

Where specified, endpoint analyses will take into account the stratification factors. The stratification factors are derived as follows:

- SLEDAI-2K score at screening (<10 points versus ≥ 10 points)
If different measurements are available for re-screened subjects, the value at re-screening is used
- Randomization (Day 1) OCS dose (<10 mg/day versus ≥ 10 mg/day prednisone or equivalent)
For the classification, the derived OCS dose rounded to 1 decimal place is used
- Region (mainland China versus not mainland China)

SLEDAI-2K score at Screening and Randomization (Day 1) OCS strata is derived programmatically from the data recorded in the eCRF.

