SLEDAI-2K score at Screening and Randomization (Day 1) OCS strata will be derived programmatically from the data recorded in the database. Region (mainland China versus non-mainland China) stratum will be taken as recorded at randomization by the Interactive voice/web response system (IXRS). Strata with low counts will be pooled with adjacent strata prior to the analysis. If a substratum within the non-mainland China region stratum has less than 20 participants (in the pooled treatment group), then all non-mainland China region strata will be pooled together. If a sub-stratum within the mainland China region stratum has less than 20 participants (in the pooled treatment group), then within the mainland China region stratum the SLEDAI-2K score <10 points sub-strata will be pooled together and the SLEDAI-2K score \geq 10 points sub-strata will be pooled together. If any of these two sub-strata within the mainland China region stratum still has less than 20 participants (in the pooled treatment group), then all China region sub-strata will be pooled together. If all not mainland China region sub-strata are pooled together and all mainland

China region sub-strata are pooled together and any of these strata has less than 20 participants (in the pooled treatment group) then all strata are pooled together.

The analysis can be described as follows:

- A. There are n_{ij} participants in each stratum, where i is the stratum, and j is the treatment group. The number of participants achieving BICLA response is x_{ij} . The proportion of participants achieving BICLA response is denoted as $p_{ij} = x_{ij} / n_{ij}$.
- B. For each stratum, the difference in proportion of participants achieving BICLA response is calculated as $d_i = p_{iA} - p_{iP}$, where A and P denote the different treatment groups (anifrolumab and placebo, respectively).
- C. Weights for each stratum, w_i , are calculated as $n_{iP} * n_{iA} / (n_{iA} + n_{iP})$. The weighted difference is calculated as:

$$WD = \frac{\sum w_i d_i}{\sum w_i}$$

- D. The standard error (SE) of the weighted difference under the null hypothesis is given by:

$$SE = \sqrt{\frac{\sum [w_i^2 \text{Var}(d_i)]}{(\sum w_i)^2}}$$

- E. For deriving the CI for the weighted difference in proportions, a correction will be applied to the variance, providing a CI with more accurate coverage. This will be applied to all strata and is derived as follows.

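### SAP 4.2.3.4 makes no use of Day 1 OCS dose (10 to 40 mg/day) in the maintained OCS-reduction analysis: the analysis is valid, but gives up precision if dose predicts success

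*SAP*

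**What the plan says.** - **Endpoint** (SAP 4.2.3.1): "Achieve an OCS dose of ≤ 7.5 mg/day prednisone or equivalent by Week 40", then held to Week 52. The target is the same for everyone.
- **Population** (SAP 4.2.3.4): the treatment difference is estimated "in subjects with baseline OCS ≥ 10 mg/day prednisone or equivalent".
- **Strata** (SAP 4.2.3.4): "For the stratified CMH analyses, the stratification factors will be reduced to SLEDAI-2K score at screening" and region.
- **OCS factor**: a single cut at 10 mg/day at randomisation (Protocol 3.5). The SAP derives the dose itself to classify participants: "For the classification, the derived OCS dose rounded to 1 decimal place is used" (SAP 4.2).
- **Upper end of dose** (Protocol 3.1, criterion 7(a), "Oral prednisone (or equivalent) monotherapy"): "Maximum daily dose: $\leq 40$ mg/day". Criterion 7(c) and Table 7 carry the same cap for combination therapy.
- **Sparse strata** (SAP 4.2.1.5): "Strata with low counts will be pooled with adjacent strata prior to the analysis", with a threshold of 20 participants, arms combined. In mainland China the first merge is across OCS levels within a SLEDAI-2K level.
- **Other analyses of this endpoint**: SAP 4.2.3.5 covers intercurrent events, a tipping point and a shift table. SAP 4.2.3.6 splits by region and SLEDAI-2K. None uses starting dose.
- **Status** (SAP 3.3.4): nominal p-value, no multiplicity adjustment.

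**The concern.** The endpoint is a fixed target reached from a variable start, so starting dose is a natural candidate to predict success. In Protocol Appendix N, Table 10 ("Example of OCS Tapering Schedule"), the 10 mg column reaches 7.5 mg in one reduction and the 40 mg column in six. Randomisation balances only the cut at 10 mg/day, so nothing in the design balances dose within the analysed subset.

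The SAP adjusts for the baseline value in its repeated-measures models, for example CLASI change (4.2.5.6) and joint counts (4.2.6.5), but not here, although the dose is already derived. At stake are the width of the interval on one of three key secondary endpoints, and the position after unblinding if the arms differ in starting dose: any adjustment chosen then would be post hoc.

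**Working it through.** **No plan figure to reproduce.** The documents give no sample size, power, response rate or dose distribution for this endpoint. Everything below except steps 1 and 2 rests on assumptions: subset N of 80, 120 or 160; response 30% on placebo and 50% on anifrolumab; 40% of the subset in the higher of two dose bands; 60% with SLEDAI-2K of 10 or more; and 80% in mainland China (the overall estimate in SAP 4.7, assumed to hold in the subset).

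**1. Cost of removing the binary factor.** All participants in the subset have the same level, so the strata, weights and estimate are unchanged. The cost is zero.

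**2. Distance to target.** 10 - 7.5 = 2.5 mg/day at one end and 40 - 7.5 = 32.5 mg/day at the other.

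**3. Analytic precision.** Let m be the response rate in an arm, q the share in the higher dose band and g the gap in response between bands. Then

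variance ratio (adjusted / unadjusted for dose) = 1 - [sum over arms of q(1-q)g²] / [sum over arms of m(1-m)].

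With q = 0.4, q(1-q) = 0.24. The denominator is 0.30×0.70 + 0.50×0.50 = 0.46.

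- g = 0.20: 1 - (2×0.24×0.04)/0.46 = 1 - 0.0192/0.46 = 0.958
- g = 0.30: 1 - (2×0.24×0.09)/0.46 = 1 - 0.0432/0.46 = 0.906
- g = 0.40: 1 - (2×0.24×0.16)/0.46 = 1 - 0.0768/0.46 = 0.833

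**4. Simulation of the SAP estimator.** 4,000 runs per setting for columns A and B, using the SAP 4.2.1.5 weighted difference with its (x+2)/(n+4) variance. The comparator is the planned analysis (SLEDAI-2K by region, with pooling). Column A adds dose bands and collapses cells under 20 by region first, then SLEDAI-2K, keeping dose last; its ranges also include a repeat simulation of the same scheme. Column B simply crosses the planned strata with the bands.

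| Gap between bands | Analytic | A: dose kept last | B: simple crossing |
|---|---|---|---|
| 0 | 1.00 | 1.01-1.02 | 1.02-1.04 |
| 20 points | 0.96 | 0.97 | 0.97-1.00 |
| 30 points | 0.91 | 0.89-0.93 | about 0.94 |
| 40 points | 0.83 | 0.84-0.86 | 0.84-0.87 |

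Power under A at N = 120: 62.0% to 64.9% at 30 points and 60.9% to 66.4% at 40 points. At N = 80: 45.7% to 47.0% and 46.8% to 51.9%. Under B the gains are smaller (N = 120, 30 points: 62.9% to 63.3%), and at N = 80 power falls slightly (46.2% to 45.0% at 30 points).

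**5. Continuous dose instead of bands.** Linear risk-difference regression with robust standard errors, assuming 35, 25, 20, 12 and 8% at 10, 15, 20, 30 and 40 mg/day. For a fall in response of 30 to 45 points from 10 to 40 mg/day, the variance ratio is 0.92 to 0.98 and power changes by about 0 to +3 points. With no gradient the ratio is about 1.01.

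**6. Chance imbalance.** The SD of the between-arm difference in the higher-band share at N = 120 (60 per arm) is sqrt(2×0.24/60) = 8.9 points. A difference above 10 points arises in about 36%, 26% and 20% of trials at N = 80, 120 and 160. With a 30-point gap, a 10-point imbalance moves the estimate by 0.30×10 = 3 points. The standard error at N = 120 is sqrt(0.46/60) = 8.8 points, so the shift is about one third of it.

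**7. Validity of the planned analysis.** Mean error was within about 0.3 points and rejection under the null was 4.6 to 5.2% at every gap tested.

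**The case against.** The strongest case for leaving the plan alone has four parts.

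- **No gradient is shown.** In Table 10 every starting dose is at 7.5 mg or below by Day 84, and Protocol 7.7.3.5 allows tapering from Week 8 to Week 40, so the number of steps is not shown to limit success. Exemption from tapering depends on disease activity, and SLEDAI-2K is kept as a stratum. This stands: the loss can only be stated conditionally.
- **Strata would be too sparse.** With about 20% outside mainland China, N = 80 to 160 leaves 16 to 32 such participants. Spread evenly over four SLEDAI-2K by dose cells, that is 4 to 8 each. Dose bands left a cell under 20 in 95 to 100% of simulated trials. This stands against the existing collapse order, which would largely pool dose away. It does not stand against an order that keeps dose last (column A) or against a continuous covariate.
- **The protocol names the method.** Protocol 8.5.2.1 applies the CMH of 8.5.1, with the randomisation factors, to this endpoint, and SAP section 2 declares no change. This stands as a cost: the change must be recorded as a departure.
- **Nothing is invalid.** This also stands. Chance imbalance in an unstratified covariate is ordinary sampling variation that the confidence interval already reflects, and the p-value is nominal.

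**Conclusion.** The gap is real and modest. The plan leaves a collected baseline variable, closely tied to the endpoint, out of every analysis of that endpoint. Under the stated assumptions, adding it changes the variance by +1 to +2% with no gradient, -3% at 20 points, -7 to -11% at 30 points and -14 to -16% at 40 points, or roughly 0 to 6 points of power. The subset size, dose split, response rates and gradient are all assumed. This is an efficiency and robustness point on a nominal key secondary endpoint.

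A reader might infer three stronger things that the documents do not support:

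- That dropping the steroid factor is a mistake. A factor with one level cannot stratify, so the SAP is right to remove it.
- That the estimate is biased or the type I error inflated. Neither was found.
- That precision is certainly lost. That needs a dose gradient, and the documents give none. With no gradient, adding dose costs slightly.

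**What to change.** Before unblinding, add Day 1 OCS dose (prednisone equivalent) to SAP 4.2.3.4 in one of two ways:

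- a pre-specified dose-band stratum, for example 10 to <20 vs 20 mg/day or more, alongside SLEDAI-2K and region, with a stated collapse order for cells under 20: region first, then SLEDAI-2K, dose kept last; or
- a continuous covariate in a standardised risk-difference model, with the variance method named. This avoids the sparse cells and the choice of cut.

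Use the same adjustment in the CMH analyses of SAP 4.2.3.5, tabulate Day 1 dose by arm in the subset, and record the departure from the protocol's randomisation-factor CMH in SAP section 2.

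Cost: SAP text and, for the band option, one derived variable; no new data. With the band option, region and SLEDAI-2K strata are pooled more often. About 1 to 2% of variance is lost if dose turns out not to be prognostic.
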